8.9. Vital Signs and Body Weight

Pulse, temperature, systolic and diastolic blood pressure, respiration rate, body weight, and BMI will be tabulated by treatment group using descriptive statistics at baseline and Day 7, Week 13, Week 26, and Week 52. Change from baseline in vital signs and body weight will be described in shift tables using mean, SE, minimum, and maximum values, by treatment group.

8.10. Estradiol

Individual E2 concentrations will be displayed graphically from pre-treatment through Week 52. E2 data will also be tabulated for each treatment group using mean, SD, median, minimum and maximum values at Day 28 and Weeks 13, 26, 30, and 52, by treatment group.

8.11. Concomitant Medications or Therapies

Concomitant medications used in 30 days prior to treatment and after treatment initiation will be summarized separately by treatment group in frequency tables, by therapeutic class and medicine category (per the WHO Drug Dictionary). Listings of medication use, including those initiated

Statistical Analysis Plan Version 5.0

Pharmacokinetics Study–Healthy Subjects

Study TV46046-WH-10159

after week 52 of follow-up (among the subset of subjects monitored for ISRs after week 52) will include indication and start and stop dates.

9. ACCEPTABILITY DATA ANALYSIS

Responses to acceptability questionnaire items at Week 26 and Week 52 will be summarized using frequency tables and compared between test and reference groups using descriptive Pearson's Chi-square tests.

10. PHARMACOKINETICS ANALYSIS

10.1. General

All pharmacokinetic analyses will be presented for the Pharmacokinetic Analysis Set unless otherwise specified.

10.2. MPA Concentrations below the LLOQ

The following rules will be applied to account for MPA concentrations below the LLOQ:

- Baseline values below the LLOQ will be imputed as 0 ng/mL
- Values that fall below the LLOQ after Day 0 will be imputed as $\frac{1}{2}$ the LLOQ when summarizing visit-specific MPA concentration data. However, any below LLOQ value that occurs after the day of a woman's last quantifiable measure (T_{last}) will be imputed as zero when computing AUC values, and ignored when computing the terminal rate constant (λ).

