1.2.2. Clinical Studies

1.2.2.1. Clinical Pharmacology Studies

The pharmacokinetics (PK) of MPA following a single subcutaneous injection of undiluted and saline diluted 120 mg TV-46046 has been evaluated in a single Phase 1 study which included 12 healthy subjects (Study TV46046-WH-10075). All subjects, except 1 in the undiluted TV-46046 group, had serum MPA levels greater than 0.20 ng/mL 24 hours after treatment initiation. Maximum observed serum drug concentration (C_{max}) in the undiluted TV-46046 group and the

saline-diluted TV-46046 group were 0.53 ng/mL and 0.97 ng/mL, respectively. Areas under the concentration curve (AUC_{0-∞}) of the undiluted TV-46046 group and the saline-diluted TV-46046 group were 94.56 days*ng/mL and 114.13 days*ng/mL, respectively. All evaluable subjects in the undiluted

TV-46046 group and all except 1 subject in the saline-diluted TV-46046 group had serum MPA concentrations exceeding 0.10 ng/mL on Day 182. The apparent half-lives of the undiluted TV-46046 group and the saline-diluted TV-46046 group were 82.87 and 42.34 days, respectively.

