1.4.2. Dosage Rationale

This study is designed to evaluate and compare the pharmacokinetics of MPA, safety and local tolerability, and acceptability of the single subcutaneous administration of one 3 doses of TV-46046 300 mg/mL (120 mg/0.4 mL, 180 mg/0.6 mL or 240 mg/0.8 mL) or 104 mg/0.65 mL of Depo-subQ Provera 104 in healthy female subjects of reproductive age. The goal is to select a dose of TV-46046 that is both safe and has PK profile consistent with contraceptive protection when injected subcutaneously every 6 months.

The selected dose range of TV-46046 was chosen to have a high probability of bracketing the dose necessary to 1) to achieve a comparable geometric mean 6-month trough concentration as the 3-month trough of the reference drug (0.35 to 0.40 ng/mL), and 2) to ensure a low (eg, 5% or less) risk of return to ovulation within 7 months of treatment injection. Both criteria are expected to be met for by a dose of TV-46046 between 120 mg/0.4 mL and 240 mg/0.8 mL based on results of Study TV46046-WH-10075 (NCT02817464), Study 702179 (NCT02456584), and the

PK/PD studies which informed the label for Depo-subQ Provera 104 ([Jain et al 2004](#), [Toh et al 2004](#)). A dose of TV-46046 in the selected range is also expected to be safe when injected subcutaneously every 6 months.

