4.4. Study Days and Visits

For purposes of analysis, the number of days post-injection on which an event occurs or an outcome is assessed will be calculated as the date of the event or outcome, minus the date of treatment initiation; a negative day indicates an event prior to study drug administration. When appropriate, fractions of study days will be computed based on the time (in hours and minutes) of a subject's injection and the time of her event or outcome assessment.

Although actual MPA sampling times will be used in applicable pharmacokinetics analyses (e.g., when computing AUC values), sampling times will be assigned to visit windows when reporting by-visit summaries of MPA concentrations (e.g., C_{182}). In order to maximize available data, the window periods used in these by-visit summaries may be wider than the target visit windows specified in the protocol (see [Table 2](#)).

Table 2. Pharmacokinetic data visit windows

Days since Treatment Initiation	Protocol Target	Visit Window	Visit-specific Analyses
1, 2	± 1 hour	+/ - 3 hours	
3, 5, 7	± 3 hours	+/ - 6 hours	
10, 12, 14, 18	± 24 hours	+/ - 24 hours	
21 and after (except days 91 and 182)	± 48 hours	+/ - 168 hours	
91, 182	± 48 hours	-84 / +168 hours	

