10.5. Noncompartmental Analysis

The following protocol-specified pharmacokinetic parameters will be estimated based on NCA: C_{max} , T_{max} , C_{91} , C_{182} , C_{210} , AUC_{0-182} , AUC_{0-210} , $AUC_{0-\infty}$, and the apparent terminal half-life (computed as $\log_e[2]/\lambda$). Additional estimates will include AUC through day of last quantifiable sample (AUC_{0-last}), and time above 0.2 ng/mL (extrapolated to infinity). Detailed rules used to estimate these parameters, and conditions that must be met to report the estimate, are as follows:

- C_{max} will be based on the maximum observed MPA concentration for subjects who a) provide at least one MPA result after their highest observed concentration and b) do not use a concomitant medication known to impact the pharmacokinetics of MPA before the occurrence of C_{max} . Values of C_{max} for subjects who fail to meet these two criteria will be considered non-evaluable and excluded from the primary pharmacokinetic analysis.
- T_{max} will be based on the day (rounded to the first decimal place) when C_{max} was initially observed. Values of T_{max} for subjects who's C_{max} is non-evaluable (per above) will be excluded from primary analyses.
- C_{91} , C_{182} , and C_{210} will be based on evaluable results in the corresponding pre-defined visit windows ([Table 2](#)). If a subject has more than one MPA result in the same visit window, then the value closest to the nominal time will be used.
- λ will be estimated as minus the slope of the terminal phase, based on the last three or more log-transformed MPA concentrations after C_{max} but on or before T_{last} , regressed on time. The specific number of time points used to compute λ will be determined based on the unweighted regression with largest adjusted R^2 . If the estimated slope is not negative, or if fewer than three time points are available for estimating λ , then no value will be reported.
- Partial AUC values will be computed using the ‘linear up log down’ rule as implemented in Phoenix WinNonLin (version 8.3 or higher). No AUC value will be reported if C_{max} was not estimable per above.
- $AUC_{0-\infty}$ will be computed as $AUC_{0-last} + C_{last}/\lambda$, where C_{last} is the last quantifiable drug concentration measurement

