10.6. Treatment Group Comparisons

Comparisons between each dose of TV-46046 and the Depo-subQ reference product will be made based on GM ratios (test/reference) and 90% CIs for GM ratios, for the following exposure parameters: C_{max} , C_{91} , C_{182} , C_{210} , AUC_{0-182} , AUC_{0-210} , $AUC_{0-\infty}$, and trough concentrations (C_{182} for each TV-46046 test group and C_{91} for the Depo-subQ provera 104 reference). Confidence intervals will be computed based on the antilog of corresponding limits for the difference in mean log concentrations (computed assuming a student-t distribution for log-transformed values). The assumptions of log-normality and homogeneity of variance will be assessed by inspection of quantile-to-quantile plots, residuals, and tests of departure from these assumptions. The lead biostatistician will use these results to determine whether either assumption is violated to a degree that alternative methods (e.g. bootstrap resampling) should be employed when reporting CIs for GM ratios.

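### If reference-arm MPA at Days 182 and 210 falls near or below the assay limit, the half-LLOQ rule can bias the C182 and C210 ratios and their 90% CIs; the readable text gives neither the LLOQ nor the reference half-life

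*SAP*

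**What the plan says.** SAP 10.2 sets the rule: "Values that fall below the LLOQ after Day 0 will be imputed as" one half of "the LLOQ when summarizing visit-specific MPA concentration data". The same section uses zero instead for values after the last quantifiable sample, but only for AUC.

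C182 and C210 are visit-specific values. SAP 4.4 gives C182 as an example of a by-visit summary, and SAP 10.5 says that C91, C182 and C210 "will be based on evaluable results in the corresponding pre-defined visit windows". SAP 10.6 lists C182 and C210 among the exposure parameters compared as GM ratios against Depo-subQ Provera 104. For the intervals: "Confidence intervals will be computed based on the antilog of corresponding limits for the difference in mean log concentrations", using a student-t distribution.

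The plan has three features that limit or disclose the problem:
- SAP 10.4 tabulates the percent below the LLOQ by group, including at Days 182 and 210.
- SAP 10.6 checks log-normality and equal variance, and lets the lead biostatistician change the CI method, with bootstrap as the example.
- SAP 10.6 also includes a trough ratio, test C182 over reference C91.

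The readable sensitivity analyses in SAP 10.7 cover the Safety Set and missing visits, not BLQ handling.

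**The concern.** Days 182 and 210 lie 91 and 119 days past the end of the reference product's 3-month interval, so its concentrations there could be close to what the assay can measure. If a sizeable share of the reference arm is BLQ, those women all receive one constant. The reference GM then partly reflects the LLOQ, the log variance is distorted, and a nominal 90% t interval need not cover 90% of the time. C182 and C210 are listed primary endpoints, and their ratios will be reported for each dose.

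**Working it through.** The documents state no figure to reproduce here, so the check is a projection under stated assumptions.

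**Inputs from the documents**
- Reference Day 91 GM, Protocol 1.4.2: "3-month trough of the reference drug (0.35 to 0.40 ng/mL"; midpoint 0.375.
- Half-lives, Protocol 1.2.2.1, for the undiluted group and then the "saline-diluted TV-46046 group were 82.87 and 42.34 days, respectively". Both are for TV-46046; using them for the reference is an assumption.
- 15 women per group (SAP 2.5).

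**Assumed**
- LLOQ of 0.02 to 0.20 ng/mL and between-woman CV of 40% or 70%.
- Test GM of 0.375 ng/mL (the dose-selection target). At an LLOQ of 0.10 or less almost no test values are BLQ, so this choice hardly changes the percentage bias.

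**Step 1, projected reference GM.** C(d) = C91 × 2^(−(d−91)/t½), with C91 from 0.35 to 0.40:
- Day 182: 0.079–0.090 ng/mL (42.34 d) or 0.163–0.187 (82.87 d).
- Day 210: 0.050–0.057 or 0.129–0.148.

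**Step 2, bias from half-LLOQ.** Let m be the true log GM, s = √ln(1+CV²), z = (ln LLOQ − m)/s and p = Φ(z), the expected BLQ share. The mean of the imputed logs is off by p·(ln(LLOQ/2) − m) + s·φ(z).

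LLOQ 0.05, Day 210, 42.34 d, CV 40%:
- GM 0.0535, s = 0.385, z = −0.17, p = 0.43.
- Shift = 0.431 × (−0.760) + 0.385 × 0.393 = −0.176.
- The ratio is multiplied by e^0.176 = 1.19, so 7.02 becomes 8.37.

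LLOQ 0.10, Day 182, 42.34 d, CV 40%:
- GM 0.0845, z = 0.44, p = 0.67.
- Shift = 0.669 × (−0.525) + 0.385 × 0.363 = −0.211.
- The ratio is multiplied by 1.23, so 4.44 becomes 5.48.

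**Step 3, coverage.** Simulated log-normal trials (at least 20,000 per setting, 15 per arm) with half-LLOQ imputation and a t-based 90% CI:

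| LLOQ | t½ (d) | Day | CV | BLQ | Ratio, true → imputed | Change | Coverage |
|---|---|---|---|---|---|---|---|
| 0.05 | 42.34 | 210 | 40% | 43% | 7.02 → 8.37 | +19% | 74% |
| 0.05 | 42.34 | 210 | 70% | 46% | 7.02 → 7.73 | +10% | 87% |
| 0.10 | 42.34 | 182 | 40% | 67% | 4.44 → 5.48 | +23% | 61–62% |
| 0.10 | 42.34 | 182 | 70% | 60% | 4.44 → 4.74 | +7% | 88% |
| 0.10 | 82.87 | 210 | 40% | 20% | 2.71 → 2.97 | +10% | 86% |
| 0.20 | 42.34 | 210 | 40% | 100% | 7.02 → 3.65 | −48% | 0% |
| 0.05 | 42.34 | 182 | 40% | 9% | 4.44 → 4.64 | +5% | 90% |
| 0.05 | 42.34 | 182 | 70% | 20% | 4.44 → 4.75 | +7% | 89% |
| 0.05 | 82.87 | 210 | 70% | 5% | 2.71 → 2.77 | +2% | 90% |
| 0.03 | 42.34 | 210 | 70% | 18% | 7.02 → 7.47 | +7% | 89% |
| 0.02 | 42.34 | 210 | 70% | 6% | 7.02 → 7.19 | +3% | 90% |

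The direction depends on the LLOQ. At 0.10 and Day 210 (42.34 d, CV 40%), 95% of the arm is BLQ yet the bias is only about +2%, because half of 0.10 happens to lie close to the assumed GM of 0.0535.

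**Step 4, trough ratio.** At Day 91 the reference GM is 0.375. With an LLOQ of 0.10, z = ln(0.10/0.375)/s = −3.43 (CV 40%) or −2.09 (CV 70%), so about 0.03% or 1.8% of values are BLQ. That is immaterial.

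**Step 5, does a censored fit help?** A censored log-normal maximum-likelihood fit recovered the reference GM at 43–46% BLQ. At about 60–67% BLQ it stayed within about 3% in trials with at least three quantifiable values. It was not reliable at 87–95% BLQ.

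**The case against.** The strongest reply is that the premise is unproven. No LLOQ appears in the readable text. The 0.10 ng/mL in Protocol 1.2.2.1 and the 0.2 ng/mL in the SAP are reporting thresholds. The larger effects mostly need the shorter half-life, which belongs to saline-diluted TV-46046. This stands: a reader might infer that reference values are expected to be BLQ at these visits, and the documents do not support that.

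Second, the 10.6 checks would probably notice. A Shapiro-Wilk test on the imputed reference arm rejected in 90–96% of simulated trials at LLOQ 0.05, Day 210, and in nearly all at 0.10, Day 182. But the response is discretionary and concerns only the CI. A percentile bootstrap covered 70% and 59% in those two settings, no better than the t interval, and it leaves the biased point estimate in place. Likewise, the percent-BLQ table discloses the problem without correcting the ratio.

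Third, a reader might infer that dose selection is at risk. It is not, on this point. The PK criterion in Protocol 1.4.2 compares the 6-month test trough with the 3-month reference trough, and that ratio is not materially affected. No hypothesis test depends on the same-day ratios, and a move from 4.4 to 5.5 or from 7.0 to 8.4 still reads as test well above reference.

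Finally, 10.6 does not itself restate how BLQ values enter. The link runs through 4.4 and 10.5, and SAP 10.8 is redacted. The link is the natural reading, but an explicit sentence is needed.

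**Conclusion.** The point holds conditionally. The readable SAP routes half-LLOQ values into the C182 and C210 GM ratios, and nothing readable corrects the resulting bias.

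With a reference half-life of 42.34 days and CV 40%, the ratio is overstated by about 19% with 74% coverage (LLOQ 0.05, Day 210), or by about 23% with 61–62% coverage (LLOQ 0.10, Day 182). At CV 70% the same two settings give roughly 7–10% and 87–88%.

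The effect is small in three situations:
- LLOQ 0.02–0.03: bias at most 7%, coverage 89% or more.
- LLOQ 0.05 at Day 182: 5–7%, coverage 89–90%.
- LLOQ 0.05 with a half-life of 82.87 days: under 3%.

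These sizes rest on the assumed LLOQ, a half-life borrowed from TV-46046, a reference C91 of 0.375 ng/mL, log-normal data and 15 per arm. The documents do not show which case applies. This is an inexpensive improvement to secondary readings of primary endpoints, not a flaw in the dose-selection comparison.

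**What to change.** - **SAP 10.2:** state the assay LLOQ. If it is low relative to the reference levels expected at Days 182 and 210, that largely settles the point.
- **SAP 10.6:** say explicitly how BLQ values enter the ratios. Whenever any value entering a C91, C182 or C210 ratio is BLQ, also estimate the GM ratio and 90% CI by a censored log-normal (Tobit) likelihood, and report it beside the half-LLOQ result. With nothing BLQ, this gives essentially the planned analysis.
- **Where most of an arm is BLQ:** report the percent BLQ and a one-sided bound rather than interpreting a point ratio. Fix the cut-off in advance; more than half of an arm is one workable choice.

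The cost is a few sentences and a standard censored-regression run. A few ratios may be reported as bounds instead of point estimates.

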10.3. Intercurrent Events

A single IcE is anticipated as possibly occurring in this study: the use of concomitant medications known to impact the pharmacokinetics of MPA. Any MPA results obtained from a subject between the initiation date of a relevant medication and the last date that the medication may have impacted the pharmacokinetics of MPA will be excluded from the Pharmacokinetics Analysis Set. This strategy corresponds to the hypothetical scenario in which the IcE did not occur when defining pharmacokinetic estimands, and the corresponding estimators will be (asymptotically) unbiased under the assumption that the excluded data are missing completely at random (i.e., the reason for use of the medication is independent of the pharmacokinetics of MPA). The precise dates of exclusion will be adjudicated by the Lead Biostatistician and Clinical Investigator in blind review whenever possible. The impact of exclusions on pharmacokinetic parameter estimators are described further in Section 10.4.

10.4. Descriptive Pharmacokinetic Summaries

Overlays of individual MPA profiles will be displayed by treatment group in the original scale and using semi-log[base 10] plots. Serum MPA concentrations will be summarized by treatment group using the mean (SD), median, minimum, maximum, percent below 0.2 ng/mL, and percent below the LLOQ at select sampling timepoints, including but not limited to: Baseline, Day 1, Day 91 (Month 3), Day 182 (Month 6), Day 210 (Month 7), and Day 364 (Month 12). Geometric Mean (GM) +/- geometric SD concentrations will be graphically displayed by treatment group at all sampling visits through Week 52 (Day 364). A graphical overlay of treatment-group GMs (with 95% CIs computed based on log-normality assumptions) will also be provided. If a subject has more than one MPA result in the same visit window (Table 2) then the value closest to the nominal time will be used when describing visit-level data. Summary measures of visit-specific

Statistical Analysis Plan Version 5.0

Pharmacokinetics Study–Healthy Subjects

Study TV46046-WH-10159

drug concentration data will be reported to the same number of decimal places as the original data.

10.5. Noncompartmental Analysis

The following protocol-specified pharmacokinetic parameters will be estimated based on NCA: C_{max} , T_{max} , C_{91} , C_{182} , C_{210} , AUC_{0-182} , AUC_{0-210} , $AUC_{0-\infty}$, and the apparent terminal half-life (computed as $\log_e[2]/\lambda$). Additional estimates will include AUC through day of last quantifiable sample (AUC_{0-last}), and time above 0.2 ng/mL (extrapolated to infinity). Detailed rules used to estimate these parameters, and conditions that must be met to report the estimate, are as follows:

- C_{max} will be based on the maximum observed MPA concentration for subjects who a) provide at least one MPA result after their highest observed concentration and b) do not use a concomitant medication known to impact the pharmacokinetics of MPA before the occurrence of C_{max} . Values of C_{max} for subjects who fail to meet these two criteria will be considered non-evaluable and excluded from the primary pharmacokinetic analysis.
- T_{max} will be based on the day (rounded to the first decimal place) when C_{max} was initially observed. Values of T_{max} for subjects who's C_{max} is non-evaluable (per above) will be excluded from primary analyses.
- C_{91} , C_{182} , and C_{210} will be based on evaluable results in the corresponding pre-defined visit windows ([Table 2](#)). If a subject has more than one MPA result in the same visit window, then the value closest to the nominal time will be used.
- λ will be estimated as minus the slope of the terminal phase, based on the last three or more log-transformed MPA concentrations after C_{max} but on or before T_{last} , regressed on time. The specific number of time points used to compute λ will be determined based on the unweighted regression with largest adjusted R^2 . If the estimated slope is not negative, or if fewer than three time points are available for estimating λ , then no value will be reported.
- Partial AUC values will be computed using the ‘linear up log down’ rule as implemented in Phoenix WinNonLin (version 8.3 or higher). No AUC value will be reported if C_{max} was not estimable per above.
- $AUC_{0-\infty}$ will be computed as $AUC_{0-last} + C_{last}/\lambda$, where C_{last} is the last quantifiable drug concentration measurement
- Time at or above 0.2 ng/mL will be computed using linear up log down interpolation if the 0.2 ng/ml threshold is crossed between two sampling time points, and log down interpolation when extrapolating to infinity.

Except for $t_{1/2}$, the primary measure of central tendency and dispersion for each pharmacokinetic parameter estimate will be the GM and geometric %CV; for $t_{1/2}$, the harmonic mean and %CV based on a jackknife estimate of SD will be reported. Additional summaries will include mean, SD, SE, median, minimum, maximum, and 95% CIs for means. Measures of AUC, T_{max} , and $t_{1/2}$ will be reported to one decimal place. Drug concentration parameter estimates (e.g. C_{max} and

Statistical Analysis Plan Version 5.0

Pharmacokinetics Study–Healthy Subjects

Study TV46046-WH-10159

C_{182}) will be summarized using the same number of decimal places as the original data. Subject listings will include each of the above parameter estimates as well as the percent of AUC extrapolated to infinity.

[figure not shown]

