2. STUDY DESIGN

2.1. General Design

This is a randomized, partially-blinded dose-range finding study to evaluate and compare the pharmacokinetics, safety, local tolerability, and acceptability of the subcutaneous administration of 3 different doses of TV-46046 300 mg/mL (120 mg/0.4 mL, 180 mg/0.6 mL, or 240 mg/0.8 mL) and the reference product Depo-subQ Provera 104 (104 mg/0.65mL) in healthy female subjects.

Study procedures and their timing in relation to treatment initiation are summarized in Table 1 of the protocol.¹ Briefly, study participation will consist of a screening period, treatment initiation and 52 weeks of primary follow-up. Enrolled subjects will provide blood samples for MPA testing at baseline (Day 0, prior to injection of study drug); Day 1, 2, 3, 5, 7, 10, 12, 14, 18, 21, and 28 post-injection; and Week 6, 8, 10, 12, 13, 15, 17, 19, 21, 23, 25, 26, 28, 30, 32, 36, 40, 44, 48, and 52 post-injection. Specimens for P and E2 measurement will be collected at Day 0 and Weeks 48, 49, 50, 51 and 52, and specimens for E2 measurement will be collected at all visits where samples for MPA or P are taken starting on Day 28.

Subjects will be evaluated for vital signs, body weight, liver enzymes, and ISRs at Weeks 1, 13, 26, and 52 post-injection; vaginal bleeding patterns will be assessed at Weeks 13, 26, and 52; acceptability will be assessed at Weeks 26 and 52; and mood will be evaluated on Days 0 and 28 and Weeks 8, 13, 17, 21, 26, 32, 36, 40, 44, 48, and 52. Subjects with unresolved ISRs at Week 52 or who report a new ISR after Week 52 will be followed every 3 months through ISR resolution or Week 78, whichever comes first (adverse events and concomitant medication use will also be evaluated at post-week 52 visits, as relevant).

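### Should SAP 10.5 require more than three points for the terminal half-life?

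*SAP*

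**What the plan says.** Under SAP 10.5, lambda is "estimated as minus the slope of the terminal phase, based on the last three or more log-transformed MPA concentrations" lying after Cmax and no later than the last quantifiable sample. The number of points "will be determined based on the unweighted regression with largest adjusted" R-squared. No value is reported when the slope is not negative, or "if fewer than three time points are available for estimating" lambda. The visible text has no minimum span, minimum fit or limit on extrapolated AUC, although the percentage of AUC extrapolated is listed for each woman.

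For half-life, "the harmonic mean and %CV based on a jackknife estimate of SD will be reported", with the median, mean, SD, minimum and maximum alongside. Under SAP 10.2, a value below the LLOQ after the last quantifiable sample "will be imputed as zero when computing AUC values, and ignored when computing the terminal rate constant". SAP 2.1 gives the late MPA sampling times as Weeks "28, 30, 32, 36, 40, 44, 48, and 52 post-injection". Half-life is a primary parameter (SAP 1.1.2) but is not among the test/reference ratios in SAP 10.6.

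**The concern.** Three points can fall on a line by chance, and adjusted R-squared rewards that however little time they cover. Weeks 44, 48 and 52 span 56 days. Protocol 1.2.2.1 reports that the half-lives for undiluted and diluted 120 mg "were 82.87 and 42.34 days, respectively", so those three samples cover only 0.68 of the longer one. The harmonic mean then gives most weight to the steepest fits.

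With 15 women per group, a few short-window fits might lower the group half-life and inflate its %CV, so that the reported spread would partly reflect the fitting rule rather than the women. Lambda also enters AUC0-inf through the extrapolated tail.

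**Working it through.** The plan states no precision for half-life, so there is no figure of its own to reproduce. Residual error, the LLOQ, the curve shape and the between-woman spread are not in the visible text and are assumed below. Triplets are for residual log SD 0.1/0.2/0.3.

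**1. Fixed windows.** SE(lambda) = sigma/sqrt(Sxx).
- Last three samples (Days 308, 336, 364): Sxx = 2 × 28² = 1,568, root 39.6.
- Last six samples (Days 224 to 364, every 28 days): Sxx = 17.5 × 28² = 13,720, root 117.1.
- The ratio of SEs is 39.6/117.1 = 0.34.
- At 20% CV (log SD 0.198) and 82.87 days, lambda = 0.6931/82.87 = 0.00836. The relative SE is 0.198/39.6/0.00836 = 60% with three points, and 0.198/117.1/0.00836 = 20% with six.

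**2. The rule as written.** Three is a floor, not the usual number. I simulated all 31 post-dose samples with a plateau at Cmax followed by mono-exponential decline. The plateau length was set to match the reported AUC: 94.56/0.53 − 82.87/0.6931 = 59 days. The SAP rule chose exactly three points in 15-19% of profiles and fewer than six in 24-28%.

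| True half-life 82.87 d, same half-life in every woman | Three-point floor | Six-point floor |
|---|---|---|
| RMSE of log half-life, no LLOQ | 0.16/0.26/0.35 | 0.05/0.11/0.16 |
| Harmonic-mean bias, no LLOQ | -2/-8/-16% | 0/-1/-4% |
| Harmonic-mean bias, LLOQ 0.05 ng/mL | +1/+1/-1% | +1/+3/+4% |
| Harmonic-mean bias, last sample Week 32, LLOQ 0.05 | -6/-19/-33% | 0/-3/-9% |

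The RMSE gain comes from the minority of short windows. Median absolute error falls only by about a quarter (ratio 0.73 to 0.81 for mono-exponential decline and for a terminal phase starting at Day 182). The median half-life under the SAP rule is off by only 0/-1/-4% without an LLOQ.

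**3. Group summaries.** The rows above give every woman the same half-life, so all apparent spread is fitting noise. With an assumed 40% between-woman CV and n = 15:
- Jackknife %CV is 40/42/47 with three points and 39/40/41 with six.
- Relative SE of the harmonic mean is 11.0/11.0/12.7% and 10.5/10.1/11.5%.
- In a run at 82.87 days and 20% residual CV, the harmonic mean was 72.0 against 76.5 days. The gap of 4.5 days is 4.5/8.06 = 0.56 of its sampling SD.

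**4. A later terminal phase.** Six points must reach back to Week 32 (Day 224). If terminal decline starts at Day 280, only Weeks 40, 44, 48 and 52 belong to it, so at least two of the six come from the earlier, slower part. With onset at Day 252, at least one does. Assuming a threefold slower decline before onset, and no LLOQ:

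| Onset, true half-life | Measure | Three-point floor | Six-point floor |
|---|---|---|---|
| Day 252, 82.87 d | median bias | +3/+5/-4% | +16/+23/+21% |
| Day 252, 82.87 d | RMSE of log half-life | 0.28/0.41/0.50 | 0.29/0.38/0.41 |
| Day 280, 82.87 d | median bias | +8/+8/+3% | +59/+58/+45% |
| Day 280, 82.87 d | RMSE of log half-life | 0.42/0.51/0.55 | 0.58/0.56/0.54 |
| Day 280, 42.34 d | RMSE of log half-life | 0.24/0.40/0.48 | 0.65/0.59/0.58 |

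With onset at Day 182 (assumed 300-day half-life before it, 82.87 days after), six points still help: RMSE 0.18 against 0.08 at 10% CV, and 0.32 against 0.17 at 20%. The ranking of the two rules therefore depends on when the terminal phase begins.

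**The case for a change.** The best case for a change is the interim analysis. It opens once at least 80% of treated women could have completed 7.5 months, close to Week 32, and it informs dose selection. Weeks 28, 30 and 32 span 28 days, or 28/82.87 = 0.34 of a half-life, and there the three-point floor pulls the harmonic mean low by up to a third at the highest assumed error. A woman who leaves early meets the same problem in the final analysis. Changing the rule would cost one sentence and one software setting, with the three-point result kept as a sensitivity analysis.

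The low pull at Week 32 is real under the early-decline profile. It does not reach the quantities on which the dose rationale rests. Protocol 1.4.2 names the 6-month trough relative to the reference's 3-month trough, and the risk of ovulation within 7 months. C91, C182 and C210 are taken from observed samples and do not use lambda. AUC0-inf does have a planned ratio, but the effect there is small: with the last sample at Week 32 and log SD 0.2, the SD of log AUC0-inf was 0.084 against 0.067.

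The low cost of the edit does not settle the matter either. A six-point primary rule would drop half-life and AUC0-inf for any woman with fewer than six usable late samples. That was at most 0.1% of simulated completers, but the figure does not cover dropouts or samples excluded for interacting medication.

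**Conclusion.** No change to the plan. The three-point floor does make some individual half-lives noisy: about one woman in six gets a three-point fit under the assumed errors. It can also lower the harmonic mean, mainly when sampling stops near Week 32. A six-point floor cuts RMSE by about half or more if log-linear decline starts early, and replaces noise with an upward bias of 16 to 59% in the median if it starts at Day 252 or 280. The documents do not give the onset for the two higher doses, and for a depot meant to last six months a late onset cannot be ruled out. Choosing between the floors is a variance-for-bias judgement on which pharmacokineticists may differ, and the SAP made it in advance with a reproducible rule.

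Little rests on the result. Half-life has no test/reference ratio, the study has no hypothesis tests, and with 40% between-woman spread the group %CV moves by 1 to 6 points. The median and range are reported beside the harmonic mean, individual semi-log profiles are plotted, and extrapolated AUC is listed per woman. Analysts can print the number of points and the span beside each half-life, or try a longer window, as ordinary reporting; neither alters a planned result. All magnitudes here depend on the assumed residual error, LLOQ, curve shape and between-woman spread.
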